### **ABSTRACT**

In the United States, patients dependent upon parenteral nutrition (PN) receive parenteral fat emulsions composed of soybean oils. Lipids are necessary in PN dependent patients due to their high caloric value and essential fatty acid content. They have been implicated in predisposing patients to PN associated liver disease. Phytosterols such as those contained in soybean oils are thought to have a deleterious effect on biliary secretion. Accumulation of lipids in the hepatic Kupffer cells may further impair liver function.

Children requiring prolonged courses of PN are at risk for developing PN associated liver disease. We hypothesize that although omega-6 fatty acid emulsions prevent fatty acid deficiency, they are not cleared in a manner similar to enteral chylomicrons and therefore accumulate in the liver and resulting in steatotic liver injury. We further hypothesize that a fat emulsion comprised of omega-3 fatty acids (i.e., fish oil) such as Omegaven® would be beneficial in the management of steatotic liver injury by its inhibition of de novo lipogenesis, the reduction of arachidonic acid-derived inflammatory mediators, prevention of essential fatty acid deficiency through the presence of small amounts of arachidonic acid, and improved clearance of lipids from the serum. Animal studies have shown that IV fat emulsions (IFE) such as fish oil that are high in eicosapentaenoic and docosahexaenoic acid reduce impairment of bile flow which is seen in cholestasis caused by conventional fat emulsions. Furthermore, we hypothesize that that intravenous omega three fatty acids will be well tolerated and might reduce the inflammatory effect in the liver of prolonged PN exposure and could potentially reverse any hepatic dysfunction due to PN/IFE use. By administering Omegaven® in place of conventional phytosterol/soybean fat emulsions we may reverse or prevent the progression of PN associated cholestasis and thus allow the patient to be maintained on adequate PN until they are able to ingest adequate nutrition enterally.

### **PURPOSE**

1. To determine the safety profile of an intravenous omega-3 fat emulsion (Omegaven®)

#### Hypothesis for Aim 1:

1.1 – After starting Omegaven® on PN, the rate of fatty acid deficiencies and imbalances will be as low as before Omegaven®. Also, the rate of triglyceride events > 400 mg/dL with Omegaven® will be similar to that seen with PN administered with soy oil IFE (conventional emulsion, i.e., Intralipid®).

1.2 – PN containing Omegaven® will be safe for patients with respect to the risk of unexpected bleeding, coagulopathies, and other adverse events.

[name], Department of Surgery, Children's Hospital & Medical Center  
[name], Department of Surgery, Children's Hospital & Medical Center  
[name], Pediatric Research Office, Dept. of Pediatrics, UNMC  
[name], Department of Biostatistics, College of Public Health, UNMC

1.3 – PN containing Omegaven® will promote more short-term growth and development than conventional fat emulsions.

2. To determine if established PN associated liver disease can be reversed or its progression halted by using a parenteral fat emulsion prepared from fish oil as measured by normalization of serum levels of hepatic enzymes and bilirubin.

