### Outcome/Endpoints

#### *Treatment safety*

Our primary outcome for treatment safety will be based on patient's essential fatty acid profile. We will compare patients before treatment with Omegaven® started and after treatment started (one month after treatment started until treatment stopped) with respect to the frequency with which triene/tetraene ratio  $> 0.2$  at any time. Primary analyses for these and all other safety outcomes will be based on a follow-up time for Omegaven® starting 30 days after baseline, i.e., 30 days after treatment started for Omegaven® patients and 2 months after the first direct bilirubin level  $< 2$  mg/dL was recorded.

Additional comparisons across treatment periods for subjects receiving Omegaven® will be aimed to assess occurrence of spontaneous bleeding (e.g., unexplained bruising, oozing from gums/incision sites), and maximum triene/tetraene ratio, minimum platelets, maximum international normalized ratio (INR), and trends in pre-albumin (age standardized levels). We will also explore trends in coagulopathies based on curves of platelets, prothrombin time (PT), partial thromboplastin time (PTT) over time, and INR. We will also describe the rate with which INR ratios were  $> 2$  (number of days/follow-up time), as a marker of coagulopathies.

Additional evaluation of Omegaven® will be performed with regards to rate in which albumin is  $> 3$  g/dL, maximum triglyceride level, rate of blood stream infections (number of positive blood cultures/follow-up-time under PN after baseline), rate of central venous catheter (CVC) infections (number of CVC infections/follow-up time and number of gram positive CVC infections/follow-up time), and occurrence of anaphylactic reactions after baseline.

We will describe trends over time for all outcomes associated with fatty acid profiles (including triene/tetraene ratios, triglycerides, total omega-6 fatty acids, total omega-3 fatty acids, total saturated, total monounsaturated, and total polysaturated fatty acids). Specific fatty acids such as arachidonic, palmoleic, palmitic, oleic, stearic, and linoleic fatty acids will also be evaluated and described.

[name], Department of Surgery, Children's Hospital & Medical Center  
[name], Department of Surgery, Children's Hospital & Medical Center  
[name], Pediatric Research Office, Dept. of Pediatrics, UNMC  
[name], Department of Biostatistics, College of Public Health, UNMC

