### *Analysis of Safety and Tolerability of Omegaven®*

All primary safety and tolerability analyses will be based on descriptive statistics. In secondary analyses, we will also assess the statistical significance of differences. The period receiving Omegaven® will start 30 days after beginning PN with Omegaven® for the main analysis. Outcomes measured in the Omegaven® will be described for a period starting 30 days after baseline.

Primary outcomes measured will include whether the triene/tetraene ratio was ever  $> 0.2$  during the intervention period and whether the INR was ever  $> 2$ . Secondary outcomes measured will include platelets, prothrombin time (PT), partial thromboplastin time (PTT), and other components of the fatty acid profile. Analysis of all categorical outcomes will be based on proportions and of all continuous outcomes will be based on means or medians of the individual mean, maximum or minimum values, as appropriate, during the respective follow-up period. Comparisons between periods (pre and post-treatment) will be performed based on paired tests, parametric or non-parametric, as appropriate. We will also explore trends over time (e.g., decreasing for INR and increasing for pre-albumin) and estimate p-values via regression models using generalized estimating equations or random effects to account for within subject correlations. When describing outcomes over time, we will explore the effect of predictors of poor hepatic outcomes, such as use of antifungal agents (e.g., amphotericin) and antidiarrheal agents (e.g., loperamide), on potential spikes.

[name], Department of Surgery, Children's Hospital & Medical Center  
[name], Department of Surgery, Children's Hospital & Medical Center  
[name], Pediatric Research Office, Dept. of Pediatrics, UNMC  
[name], Department of Biostatistics, College of Public Health, UNMC

We will also evaluate nutritional outcomes including difference in weight-for- age Z-scores and height-for-age Z-scores from baseline to the moment in which the child starts enteral feeding and to the moment in which the child receives less than 10% of their calories from PN. Using linear regression, we will explore adjustment for baseline alternative predictors of interest. Trends over time in Z-scores will also be explored using regression with repeated measure methods.

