#### *Statistical Power and Sample Considerations*

The number of subjects included in the study will be based on a compassionate use protocol and not on study power considerations. The primary safety analysis will be descriptive and not based on statistical significance. However, in Table 4 we outline power to detect several differences in the frequency of adverse events, assuming 20, 25, or 30 patients, diverse proportion of subjects with adverse event in either treatment period and not with the adverse event in either treatment period and not with the adverse event in the other (proportion of discordant pairs), for a two-sided 5% significance level McNemar's tests.

For lower proportions of discordant pairs, we would generally attain close to 80% power in McNemar's test. Even for higher proportions of discordant pairs, assuming the high differences between before and after treatment that we expect to observe, e.g., 50% or more, 80% power can be attained in McNemar's test (Table 4).

Table 4—Power to detect varying differences in proportions before and after treatment with Omegaven® in a McNemar's test. All calculations based on an alpha significance level of 0.05

Difference between proportions	Proportion of discordant pairs	McNemar's Test		
		Sample Size		
		20	25	30
30%	40%	59%	72%	81%
	60%	44%	55%	63%
50%	60%	92%	97%	99%
	80%	79%	88%	93%
80%	85%	>99%	>99%	>99%
	95%	>99%	>99%	>99%

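### Hypothesis 1.1 claims no increase in fatty acid deficiency, but neither the secondary difference tests nor Table 4 address that claim, and the expected 50-point differences do not fit it

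*Protocol*

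**What the plan says.** Under Aim 1, hypothesis 1.1 states that after the switch "the rate of fatty acid deficiencies and imbalances will be as low as before Omegaven". Hypothesis 1.2 adds that treatment will be safe with respect to bleeding, coagulopathy and other adverse events. No largest acceptable increase is given.

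The Treatment safety section makes the essential fatty acid profile the primary safety outcome and defines a within-patient comparison: "We will compare patients before treatment with Omegaven® started and after treatment started". The measure is how often the triene/tetraene ratio exceeds 0.2 at any time.

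The section on analysis of safety and tolerability begins: "All primary safety and tolerability analyses will be based on descriptive statistics". It continues: "In secondary analyses, we will also assess the statistical significance of differences". On method it says: "Comparisons between periods (pre and post-treatment) will be performed based on paired tests, parametric or non-parametric, as appropriate".

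The section on statistical power repeats the descriptive stance: "The primary safety analysis will be descriptive and not based on statistical significance". It says that enrolment follows compassionate use rather than power. It then offers Table 4, the power of a two-sided 5% McNemar test for before/after differences of 30, 50 and 80 points, "assuming 20, 25, or 30 patients". It comments that adequate power can be reached "assuming the high differences between before and after treatment that we expect to observe, e.g., 50% or more".

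**The concern.** A claim that a rate has not risen can be supported by an estimate of the change with an upper confidence limit, read against a stated tolerable increase. It cannot be supported by failing to reject a hypothesis of no difference, least of all in a small cohort. The protocol fixes a test and a power table that both look for differences, and the table stops at 30 points. A rise in deficiency of 10 to 20 points lies outside it.

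The comment about expected differences adds a second problem. A power argument that relies on before/after changes of 50 points or more sits badly beside hypotheses that predict no rise in deficiency and acceptable safety.

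At stake is the primary safety outcome. Bare proportions with a non-significant paired test beside them would leave the trial unable to say whether its own hypothesis was supported, and a clinically important rise could go unrecognised.

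**Working it through.** **Inputs.** From the protocol: paired before/after comparison, McNemar's test, two-sided 5%, scenarios N = 20, 25 and 30, and the Table 4 grid. Assumed here: all discordant pairs are newly deficient children and none resolves (one-way discordance); true rises of 10, 15 and 20 points. The protocol does not say which form of McNemar's test is meant, so two are shown.

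**Step 1. Table 4.** Let the number of discordant pairs be Binomial(N, pD), with probability (pD + d)/(2·pD) that a discordant pair lies in the favoured direction, where d is the difference. Power at N = 20/25/30:

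| d / pD | Table 4 | Exact, two-sided 5% | Uncorrected chi-square, two-sided 5% | Exact, one-sided 5% |
|---|---|---|---|---|
| 30% / 40% | 59/72/81% | 46/60/71% | 60/71/80% | 59/72/81% |
| 30% / 60% | 44/55/63% | 31/41/50% | 40/50/59% | 44/55/63% |
| 50% / 60% | 92/97/99% | 86/94/98% | 91/96/99% | 92/97/99% |
| 50% / 80% | 79/88/93% | 68/79/87% | 76/86/92% | 79/88/93% |

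No two-sided version tried reproduces the whole table. A one-sided 5% exact test reproduces every cell, including the 80-point rows. Against the two-sided exact test, the stated power is too high by up to about 14 points (55% against 41%).

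**Step 2. Smallest significant result.** With k newly deficient children and none resolved:
- Exact: p = 2 × 0.5^k. k = 5 gives 0.0625 and k = 6 gives 0.031, so 6 are needed.
- Uncorrected chi-square: the statistic is k on 1 df. k = 4 gives p = 0.046, so 4 are needed.
- Continuity-corrected chi-square: k = 5 gives p = 0.074 and k = 6 gives 0.041, so 6 are needed, as in the exact test.

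Five new cases are 25%, 20% or 17% of 20, 25 or 30 children.

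**Step 3. Power for rises below Table 4's range.** With one-way discordance this is P(X ≥ 6) or P(X ≥ 4) for X ~ Binomial(N, rise):

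| True rise | Exact, N = 20/25/30 | Uncorrected chi-square, N = 20/25/30 |
|---|---|---|
| 10 points | 1/3/7% | 13/24/35% |
| 15 points | 7/16/29% | 35/53/68% |
| 20 points | 20/38/57% | 59/77/88% |

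**Step 4. Best possible result.** With no newly deficient child, the one-sided 97.5% upper bound on the risk of new deficiency is 1 − 0.025^(1/N): 16.8% at 20, 13.7% at 25, 11.6% at 30.

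**Step 5. The 50-point expectation.** Two proportions can differ by 50 points only if one of them is at least 50%. Applied to deficiency, a rise of that size contradicts hypothesis 1.1. A fall of that size needs a rate of at least 50% beforehand, which does not match a hypothesis that treats the earlier rate as low. Applied to bleeding or coagulopathy, a 50-point rise contradicts hypothesis 1.2, and a 50-point fall again needs a rate of at least 50% before treatment. The text names neither outcome nor direction, so no reading can be confirmed.

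**The case against.** The strongest reply is that the protocol does not rest safety on a test. It says twice that the primary safety analysis is descriptive, and it makes significance testing secondary. A reader might infer that a non-significant McNemar result will be reported as proof of safety. Nothing in the document states such a rule, and that inference should not be attributed to it.

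Two other strong readings also fail. The figures 20, 25 and 30 are scenarios for Table 4, not a planned sample size. The expected 50% difference is not stated for fatty acid deficiency: the power section speaks of adverse event frequency in general, and the paired safety outcomes also include INR above 2 and bleeding.

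The power figures depend on the form of the test. The uncorrected chi-square is rough with so few discordant pairs, but it gives much higher power than the exact test, so the range has to be shown. At 30 patients it would detect a 20-point rise with probability 88%.

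Finally, a margin and an interval method are often left to the statistical analysis plan, and a formal non-inferiority criterion is demanding for a non-randomized compassionate-use cohort. That is fair, and the absence of a margin alone would not be a finding. What remains is that the protocol itself chose the hypothesis, the kind of test and the power table. The last two do not bear on the first, and a descriptive analysis without an interval does not bear on it either.

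**Conclusion.** The point holds as a mismatch between hypothesis and analysis, not as a flawed primary test. Hypothesis 1.1 is a no-increase statement on the primary safety outcome. The secondary difference tests and Table 4 do not address it, and a non-significant result could not support it. For a true 10-point rise, significance would be missed with probability of at least 65% in every scenario (100 − 35) and up to 99% (100 − 1). For a 20-point rise the miss probability runs from 12% (uncorrected chi-square, N = 30) to 80% (exact test, N = 20). These figures assume that no child's deficiency resolves and use Table 4's scenario sizes.

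Separately, and without any calculation about rises, the expectation of differences of 50% or more does not fit hypotheses 1.1 and 1.2 as written. The mismatch between Table 4's two-sided label and its figures is a further reason to revise the table. The change should be made; it does not put the conduct of the study in question.

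**What to change.** - In the descriptive primary safety analysis, report the paired before/after difference in the proportion with a triene/tetraene ratio above 0.2, with its 95% confidence interval.
- State that a non-significant test will not be taken as support for hypothesis 1.1. Claim no increase only if the upper limit lies below an increase that the sponsor sets in advance. Otherwise report the estimate and interval without that claim.
- Add to Table 4, or put in its place, the interval precision expected at 20, 25 and 30 patients. If the power figures stay, name the form of McNemar's test and correct either the sidedness or the values.
- Give the outcome and direction to which the expected 50% difference refers, and reconcile it with hypotheses 1.1 and 1.2, or delete it.

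The cost is analysis wording and one table; no extra patients or data are needed. The downside is a more cautious safety conclusion that may stay inconclusive at these sizes. As an illustration with assumed margins (true difference 0, one-sided 2.5%, 80% power, normal approximation), N = (1.96 + 0.84)² × pD / margin². With 10% or 20% of pairs discordant this gives 79 or 157 patients for a 10-point margin, 35 or 70 for 15 points, and 20 or 40 for 20 points.

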### Dose Modification

#### Lipid Intolerance

If lipid intolerance develops, defined as serum triglyceride levels > 200 mg/dL, the following will be considered prior to reducing the dose:

- a) If the level was obtained while the patient was receiving a continuous 24-hour infusion of Omegaven®, the total dose should be infused over 20 hours, and a repeat serum triglyceride level obtained prior to resuming the infusion 4 hours later.
- b) Other sources of lipid intolerance should be considered and addressed (drugs, renal disease)

If the triglycerides continue to remain high despite the aforementioned interventions, a dosage reduction of 25% of the current dose will be considered.

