**Patients will be withdrawn from the study for any of the following:**

- a) Toxicity considered unacceptable by the Principal Investigator (i.e. Evidence of burr cell anemia (reported toxicity); Continued lipid intolerance (triglyceride >200) despite dose reduction attempts and administration modification; evidence of coagulopathy (INR > 2.0)).
- b) Patient/guardian requests to discontinue treatment and/or observation for any reason.
- c) A suitable organ has been located and the patient is able to undergo a liver or liver/intestinal transplant.
- d) Decision by the Principal Investigator that termination is in the patient's best medical interest.
- e) Patient is lost to follow up.

In the event that a patient is withdrawn from the protocol, study staff will document the date of withdrawal, the reason for withdrawal, and the results of all measurements of interest made up to date of withdrawal.

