#### **Safety Labs Schedule:**

Lab Name	Schedule*
Serum triglycerides	At baseline, weekly for 4 weeks, monthly thereafter
Coagulation labs	At baseline, weekly until direct bilirubin is < 2mg/dL, monthly thereafter
Fatty acid profile	At baseline, monthly thereafter

\*minimum requirements, may be performed more frequently for routine clinical care

If under the discretion of the principal investigator the patient is able to return home and receive Omegaven®, the patient is required to return to Children's Hospital & Medical Center every 2 months or other mutually agreed upon schedule for evaluation and follow up. The Principle Investigator also requires for arrangements to be made through the patient's home health care agency for the required weekly or monthly blood draws the patient will need while at home in order to remain on Omegaven®. The lab results then must be faxed to Children's Hospital & Medical Center in a timely manner. Additionally, measures will be taken to decrease the chance of administration errors when Omegaven® is given in the home. Families will be provided with a letter outlining strategies for reducing medication administration errors, such as independent double-checks.

Dose reduction will occur if there is evidence of lipid intolerance (serum triglycerides  $>$  200mg/dL) or evidence of bleeding. Growth indices include weight, length, and head circumference will also be monitored.

Other standard care laboratory results will be captured for the Omegaven® protocol. These are listed along with the standard schedule in Table 3.

The frequency of laboratory monitoring may be reduced to monthly or as clinically necessary, for patients who have been on a stable regimen of Omegaven® for a minimum of 4 months and whose serum bilirubin and hepatic enzymes have normalized.

The study team will round on all inpatients receiving Omegaven® therapy. A complete comprehensive case review for all inpatients receiving Omegaven® therapy under the compassionate-use protocol and any outpatients issues will be discussed among [name], [name], and the study coordinator. All pertinent medical, nutritional, and psychosocial outpatient information will be reviewed during these case reviews.

[name], Department of Surgery, Children's Hospital & Medical Center  
[name], Department of Surgery, Children's Hospital & Medical Center  
[name], Pediatric Research Office, Dept. of Pediatrics, UNMC  

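### Hypothesis 1.1 rests on triglyceride events > 400 mg/dL, but no listed outcome counts them, the main window opens at day 30, and Omegaven is already modified on a > 200 mg/dL criterion

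*Protocol*

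**What the plan says.** - **Hypothesis for Aim 1 (1.1):** the safety claim is that "the rate of triglyceride events > 400 mg/dL with Omegaven" "will be similar to that seen with PN administered with soy oil IFE". No margin for similarity is given, and the 400 mg/dL figure appears nowhere else in the protocol.
- **Treatment safety (Section D):** among the additional evaluations is "maximum triglyceride level, rate of blood stream infections". Triglycerides also appear in a list of fatty-acid outcomes whose trends will be described. Neither item has a cut-off or an event count. Primary analyses of all safety outcomes start 30 days after baseline.
- **Analysis of Safety and Tolerability:** the primary outcomes are the triene/tetraene ratio and INR. The day-30 start is repeated for the main analysis.
- **Lipid Intolerance (Dose Modification):** "If lipid intolerance develops, defined as serum triglyceride levels > 200 mg/dL", infusion timing and other causes are looked at first. If levels stay high, "a dosage reduction of 25% of the current dose will be considered".
- **Safety Labs Schedule:** the same > 200 mg/dL criterion is given a firmer consequence: "Dose reduction will occur if there is evidence of lipid intolerance". Minimum triglyceride sampling is at baseline, weekly for 4 weeks, then monthly.
- **Withdrawal criteria (Section G):** one example of unacceptable toxicity is "Continued lipid intolerance (triglyceride >200) despite dose reduction attempts and administration modification". For withdrawn children, measurements are documented up to the withdrawal date.

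**The concern.** The hypothesised event lies at twice the level on which the protocol acts. Some children heading towards 400 mg/dL will have had the infusion re-timed or reduced, or will have left the study, before they could reach it. The analysis window then omits the first month, when required sampling is densest. No listed outcome counts either the hypothesised event or the protocol's own definition of lipid intolerance.

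What is at stake is how a reassuring result would be read. A few or no events > 400 could be reported as tolerance similar to soy oil while a material share of children exceeded 200 and needed changes to treatment. The lipid-tolerance part of Aim 1 would then be answered only for the drug as managed, after day 30, in children still on it.

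**Working it through.** The protocol gives no expected rate, margin or power for triglyceride events, so there is no figure to reproduce. The check sets its statements side by side.

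**1. Cut-off and outcome.** Hypothesis 1.1 uses > 400. The endpoint list has a maximum and a trend. Whether a child was ever > 400 follows from that child's maximum. An event rate does not, because one maximum per child gives neither the number of events nor the time at risk.

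**2. Action level against event level.** 200 / 400 = 0.5. Action starts at half the hypothesised level, so the > 400 rate on Omegaven is a rate under active management.

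**3. Window.** Weekly checks for 4 weeks end at about day 4 × 7 = 28. The main window opens at day 30, so essentially all the required weekly checks fall outside it and the required minimum inside it is monthly. The Reversal Study Lab Schedule adds a weekly lipid panel while direct bilirubin is ≥ 2 mg/dL on Omegaven, so some children will have denser data after day 30. That does not recover the first month.

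**4. Truncated follow-up.** A child withdrawn for persistent levels > 200 contributes values only up to that date. A child withdrawn before day 30 contributes nothing to the main window. If withdrawn children are those most likely to exceed 400, the remaining follow-up time is weighted towards children at lower risk.

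**5. Comparator.** The dose and withdrawal rules are written for Omegaven. No triglyceride rule is stated for soy oil, and required sampling starts at the Omegaven baseline. The source of the soy-oil rate, and how triglycerides were managed in that period, are therefore not given.

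**6. What a zero count would show.** The one-sided 95% upper limit for 0 events in n children is 1 − 0.05^(1/n). For the sample sizes in Table 4:
- n = 20: 13.9%
- n = 25: 11.3%
- n = 30: 9.5%

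**7. How far the two measures could diverge (assumed numbers).** Suppose 2 to 10 of 25 children exceed 200 and none is recorded > 400. The hypothesised event reads 0/25 = 0%, while intolerance by the protocol's definition reads 2/25 = 8% to 10/25 = 40%. This takes the absence of events > 400 as given. It shows only that the two measures can tell different stories, and does not predict that they will.

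**The case against.** An action level set below a severe-event level is not in itself a contradiction, and the rate of severe events under the regimen as managed is a legitimate safety question. That stands, and it is why > 400 should be kept.

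A reader might infer that children are withdrawn as soon as they exceed 200. The protocol does not say so: withdrawal follows only continued elevation after dose and administration changes, as an example of toxicity the investigator judges unacceptable. A child can stay on treatment above 200 across several measurements.

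A reader might also infer that the hypothesis would be met by the management rule rather than by the drug. That does not follow. The rule reacts to measured values, and under the minimum monthly sampling a level can pass from below 200 to above 400 between draws. Nor can bias against soy oil be established from silence. The same standards of care apply to all children on parenteral nutrition, and if soy-oil triglycerides were managed in a similar way the bias would be smaller.

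Deriving ever > 400 from the listed maximum is the kind of detail an analysis plan can supply. Reasons for withdrawal are recorded, cases are reviewed at least monthly, and adverse events are collected from the first infusion, so intolerance would not be invisible to the investigators. These safeguards do not make it a reported outcome, and they do not change the day-30 start that the protocol itself fixes.

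**Conclusion.** The point holds in a limited form. The protocol sets a safety hypothesis on an event that no listed outcome counts, observes it under intervention at half its level, opens the main window after essentially all the required weekly checks, and documents withdrawn children only to the withdrawal date. A low or similar > 400 rate could partly reflect management and truncated follow-up and could not be credited to the drug alone.

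The size of any bias cannot be stated, because the protocol gives neither triglyceride event rates nor the management of soy-oil triglycerides. The only firm numbers are the factor of two between the levels, day 28 against day 30, and upper limits of 9.5% to 13.9% for a zero count in 30 to 20 children. Triglycerides are not a primary safety outcome and the primary safety analyses are descriptive, so the trial's main safety results are unaffected. What changes is what can be concluded about lipid tolerance.

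**What to change.** 1. Keep > 400 mg/dL as the hypothesised event and add it to the Treatment safety outcomes, both as ever > 400 per child and as events per follow-up time.
2. Add the proportion and rate of first triglyceride > 200 mg/dL with 95% CIs, counted from first infusion as well as in the day-30 window. Compare with the soy-oil period only where values exist for that period.
3. Report dose changes and withdrawals for triglycerides separately, as descriptive counts for Omegaven. They should not enter a between-period composite, because the protocol defines no soy-oil counterpart.
4. State beside the result that the > 400 rate was measured under active management at > 200.
5. Reconcile the Lipid Intolerance section, where a reduction is something to consider, with the Safety Labs Schedule, where it takes place. This is a request for consistency and proposes no change to any action threshold.

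The cost is protocol and analysis wording and slightly more analysis work. Triglycerides on Omegaven are already measured, so no extra sampling is needed. The reported intolerance rate will be higher than the > 400 rate alone would suggest.
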